11.0 Criteria for Response

For MDS, the International Working Group criteria will be use to assess response (11).

Remission is calculated from date of first response until relapse. Survival is calculated from start of therapy until death from any cause.

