1.0 Objectives

Primary: To determine the safety of nivolumab and lirilumab, as single agents or in combination and with 5-azacitidine, in patients with MDS.

Secondary:

1. To explore the clinical activity of nivolumab and lirilumab, as single agents or in combination and with 5-azacitidine, in patients with MDS including response, overall survival and progression free survival
2. To explore the biological activity of these compounds in patients with MDS.

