15.0 Statistical Considerations

This is a Phase II open-label study designed to determine the safety and efficacy of nivolumab and lirilumab, as single agents or in combination and with 5-azacitidine, in patients with myelodysplastic syndromes (MDS). Two different patient groups (lower risk MDS and High MDS) with 2 cohorts each will be study. Each cohort will be composed of N=20 patients. Accrual will be parallel for each patient group.

The primary efficacy outcome for each cohort is the overall response rate (ORR) defined as CR + PR + hematological improvement (HI). Overall response will be assessed after 6 cycles of treatment; cycle length is 28 days. A maximum of 20 total evaluable patients will be enrolled in each cohort (N=80).

Lower Risk MDS cohorts: cohorts (1 and 2): each cohort separately

The target ORR with the experimental treatment (i.e. lirilumab alone or in combination with nivolumab) is 70%, assuming the standard treatment ORR is 50%. The regimen of the experimental treatment will be considered worthy of further investigation if it elicits an increase in ORR to 70% with acceptable toxicity. A >30% therapy related non-hematological grade 3/4 toxicity rate is considered unacceptable. Thus, interim

monitoring rules, assuming the prior distributions above, were constructed that meet the following two conditions,

- 1) Stop if $\text{Prob}\{p(\text{ORR}, E) < p(\text{ORR}, H) + 0.20 \mid \text{data}\} > 0.95$, or
- 2) Stop if $\text{Prob}\{p(\text{TOX}, E) > 0.30 \mid \text{data}\} > 0.975$,
- 3) where $P(\text{ORR}, E)$ and $P(\text{TOX}, E)$ are the true ORR and toxicity rates for the combination treatment, and $p(\text{ORR}, H)$ is the true ORR rate of the standard treatment. The first rule provides for stopping the study if the data suggest that it is unlikely (i.e., probability < 5.0%) that ORR rate of the experimental treatment is greater than the ORR rate of standard treatment by 20.0%. The second condition will stop the study early if excessive therapy-related non-hematological grade 3/4 toxicity (>30.0%) is highly probable (i.e., probability >97.5%) for the experimental treatment. Monitoring for toxicity and futility will start when the first patient has been evaluated, and cohort size for future evaluations is 5.

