All patients who received any dose of the study agent will be included in the analysis for efficacy and safety. Demographic/clinical characteristics (i.e. including duration of response) and safety data of the patients will be summarized using descriptive statistics such as mean, standard deviation, median and range. For the primary efficacy analysis, we will estimate the ORR for the experimental treatments, along with the 95% credible intervals. The association between ORR and patient's clinical characteristics will be examined by Wilcoxon's rank sum test or Fisher's exact test, as appropriate. Toxicity type, severity and attribution will be summarized for each patient using frequency tables. The distribution of time-to-event endpoints (PFS and OS) including overall survival and event free survival will be estimated using the method of Kaplan and Meier. Comparisons of time-to-event endpoints by important subgroups will be made using the log-rank tests. Paired t-tests will be used to determine the immunological and molecular changes in the peripheral blood and bone marrow from baseline to the time of response, and to the time of disease progression.

16. Confidentiality Plan

Confidentiality will be maintained via codification of data collected and restriction of access to the data. In particular, to be authorized to use the PDMS database, M. D.

Anderson employees must have an institutional USERID assigned through the Information Services Security Department. State regulations for database computer access are followed. ALL database analysts regularly log and monitor the system access and log-in activity. All unsuccessful attempts to access the ALL database are logged to a file that is reviewed daily by the ALL database coordinator. If the user has updated patient data, they will be prompted for the password upon exiting the ALL database. If the password is not verified, an automated e-mail is sent to the ALL database coordinator, and a log is created. Users are required to change their password every three months. The passwords are stored in an encrypted format.

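### Remission ends only at relapse, so death in remission and loss of a lesser response have no end date, and the planned descriptive summary of response duration cannot handle either

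*Combined protocol and SAP*

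**What the plan says.** Section 11.0 defines two intervals in consecutive sentences. For remission: "Remission is calculated from date of first response until relapse". For survival: "Survival is calculated from start of therapy until death from any cause". Death is an end event in the second and is absent from the first.

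The Statistical Analysis Plan in section 15.0 places response duration among patient characteristics: "Demographic/clinical characteristics (i.e. including duration of response) and safety data of the patients will be summarized using descriptive statistics". The statistics listed are mean, SD, median and range. Kaplan-Meier is assigned to other endpoints: "The distribution of time-to-event endpoints (PFS and OS) including overall survival and event free survival will be estimated". Duration of response is not in that list, and neither progression free nor event free survival is defined, so no rule for deaths can be borrowed from them.

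The responses counted are wider than remissions: section 15.0 has "overall response rate (ORR) defined as CR + PR + hematological improvement (HI". The secondary objective in section 1.0 covers clinical activity "in patients with MDS including response, overall survival and progression free survival"; it does not name duration of response separately.

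**The concern.** Taken literally, the remission rule leaves a responder who dies without relapse with neither an end date nor an event. The same question arises for a patient whose only response was hematological improvement and who loses it, because relapse does not clearly describe that. The plan also has no rule for responders still in response at the data cut.

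Section 2.0 gives the limited duration of response to hypomethylating agents as a reason for the trial, so readers will look at how long responses last. Death in remission is plausible in a marrow-failure disease: section 8.3 lists febrile neutropenia in 16.4% of azacitidine-treated patients. With few responders per cohort, two or three such deaths can move a median, and the convention could be chosen after the data are seen.

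**Working it through.** **Plan's own figure.** There is none: the documents give no median, event count or follow-up for response duration. The stopping boundaries and all 25 operating-characteristic entries in section 15.0 were recalculated and agree with the plan. None of them uses the remission definition.

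**Inputs from the documents.** Each cohort has 20 patients; the reference response rate is 50% and the target 70%. Responders per cohort: 20 × 0.50 = 10 and 20 × 0.70 = 14. Once all remissions have ended, two deaths among 14 are 14% of ending events and three among 10 are 30%.

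**Assumptions, not in the documents.** Constant hazards h_r (relapse) and h_d (death in remission); d = h_d/(h_r + h_d); relapse-only median 12 months; d = 10%, 20% or 30%.

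**Step 1: deaths censored in a Kaplan-Meier curve.** The curve's median is ln2/h_r. The median time to relapse or death is ln2/(h_r + h_d). The ratio is 1/(1-d).

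| d | Reported median | Relapse-or-death median, 12 × (1-d) | Ratio |
|---|---|---|---|
| 10% | 12.0 | 10.8 | 1.11 |
| 20% | 12.0 | 9.6 | 1.25 |
| 30% | 12.0 | 8.4 | 1.43 |

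**Step 2: other conventions that fit the text, at d = 20%.** The total hazard is λ = ln2/9.6 = 0.0722 per month. Every responder is followed for F months from first response.

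- *Relapsers only.* With constant hazards, time to the first event does not depend on its type, so relapse times follow λ truncated at F. The median solves 1 - exp(-λt) = 0.5 × (1 - exp(-λF)). For F = 12, 24 and 36 this gives 4.7, 7.3 and 8.6 months, and 9.6 only with complete follow-up.
- *All responders, clock stopped at death or last follow-up.* The median is 9.6 when F exceeds 9.6 months. The mean, (1 - exp(-λF))/λ, is 8.0, 11.4 and 12.8 months for F = 12, 24 and 36, against a true mean of 1/λ = 13.85.
- *Deaths carried forward as continuing remission, F = 24.* The median solves 0.8 × (1 - exp(-λt)) = 0.5, so t = -ln(0.375)/0.0722 = 13.6 months.

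Against a relapse-or-death median of 9.6 months, the reported median therefore runs from 4.7 to 13.6, depending on the convention and the follow-up.

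**The case against.** A reader might infer from the remission sentence that response duration will be overstated, and that the more toxic regimen will look better because its short remissions are removed. The documents support neither inference. The 1/(1-d) inflation needs a time-to-event curve with deaths censored, and section 15.0 plans no such curve for this endpoint. Under constant hazards, remissions ending in death are no shorter than those ending in relapse, so dropping them does not lengthen the median; with limited follow-up, a relapsers-only median is too short. Section 15.0 assesses each cohort separately and plans no comparison of response duration between regimens.

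Importance is also limited. Duration is not a separately named objective, and deaths are still counted in overall survival. Precision is poor in any case: even if every responder had an event, a 95% interval for an exponential median, with factor exp(±1.96/√events), spans about 0.54 to 1.86 times the estimate with 10 events and 0.59 to 1.69 times with 14. Time to relapse with death as a competing event is a legitimate quantity in its own right.

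All of that stands against a claim of known direction or size. It does not supply the missing rule. Section 11.0 refers to the International Working Group criteria for assessing response, but their content is not reproduced, and the reference number given leads to a laboratory paper on azacitidine in cultured cells. Wide intervals are no reason to leave the endpoint undefined.

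**Conclusion.** The point holds as a defect of definition and method. Relapse is the only end event, two kinds of responder can lack an end date, and the planned summary has no means of dealing with incomplete durations. The direction of distortion cannot be determined from the documents. It is upward by 11%, 25% or 43% at d = 10%, 20% or 30% if deaths are censored in a curve; under other conventions the median can be too short or about right. These sizes rest on constant hazards, a 12-month median and the chosen values of d, all of them assumptions. The consequence is confined to a descriptive summary: overall response rate, stopping rules, sample size and overall survival do not change. The correction is worth making because a published response duration could not be interpreted without it.

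**What to change.** In section 11.0, replace the remission sentence with a definition along these lines: *duration of response runs from first response to the earliest of relapse, loss of response or death from any cause; responders still in response are censored at their last disease assessment.* Section 10.0 already uses loss of response as a term, and it gives partial and hematological-improvement responders an end event. State which assessments count, since section 10.0 leaves marrow sampling after a response to the treating physician.

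In section 15.0, move duration of response from the descriptive summary to the Kaplan-Meier list, for responders only. Cumulative incidence of relapse, with death as a competing event, can be added as a supportive display.

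The cost is one sentence in section 11.0 and one line in the analysis plan. Death dates are already needed for overall survival. The downside is that the reported duration may be somewhat shorter, since deaths unrelated to the disease will also end a response.

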12.0 Reporting of Adverse Events

Baseline events will be recorded in the medical history section of the case report form and will include the terminology event name, grade, and start date of the event.

Baseline events are any medical condition, symptom, or lab abnormality present before the informed consent is signed. If exact start date is unknown, month and year or year may be used as the start date of the baseline event.

The maximum grade of the adverse event will be captured per cycle.

Serious Adverse Event Reporting (SAE) Language for M. D. Anderson-sponsored IND Protocols

An adverse event or suspected adverse reaction is considered “serious” if, in the view of either the investigator or the sponsor, it results in any of the following outcomes:

- Death
- A life-threatening adverse drug experience – any adverse experience that places the patient, in the view of the initial reporter, at immediate risk of death from the adverse experience as it occurred. It does not include an adverse experience that, had it occurred in a more severe form, might have caused death.
- Inpatient hospitalization or prolongation of existing hospitalization
- A persistent or significant incapacity or substantial disruption of the ability to conduct normal life functions.
- A congenital anomaly/birth defect.

Important medical events that may not result in death, be life-threatening, or require hospitalization may be considered a serious adverse drug experience when, based upon appropriate medical judgment, they may jeopardize the patient or subject and may require medical or surgical intervention to prevent one of the outcomes listed in this definition. Examples of such medical events include allergic bronchospasm requiring intensive treatment in an emergency room or at home, blood dyscrasias or convulsions that do not result in inpatient hospitalization, or the development of drug dependency or drug abuse (21 CFR 312.32).

- **Important medical events as defined above, may also be considered serious adverse events. Any important medical event can and should be reported as an SAE if deemed appropriate by the Principal Investigator or the IND Sponsor, IND Office.**
- All events occurring during the conduct of a protocol and meeting the definition of a SAE must be reported to the IRB in accordance with the timeframes and procedures outlined in “The University of Texas M. D. Anderson Cancer Center Institutional Review Board Policy for Investigators on Reporting Unanticipated Adverse Events for Drugs and Devices”. Unless stated otherwise in the protocol, all SAEs, expected or unexpected, must be reported to the IND Office, regardless of attribution (within 5 working days of knowledge of the event).
- **All life-threatening or fatal events**, that are unexpected, and related to the study drug, must have a written report submitted within **24 hours** (next working day) of knowledge of the event to the Safety Project Manager in the IND Office.
- **Unless otherwise noted, the electronic SAE application (eSAE) will be utilized for safety reporting to the IND Office and MDACC IRB.**
- **Serious adverse events will be captured from the time of the first protocol-specific intervention, until 30 days after the last dose of drug, unless the participant withdraws consent. Serious adverse events must be followed until clinical recovery is complete and laboratory tests have returned to baseline, progression of the event has stabilized, or there has been acceptable resolution of the event. Additionally, any serious adverse events that occur after the 30 day time period that are related to the study treatment must be reported to the IND Office. This may include the development of a secondary malignancy.**

Reporting to FDA:

- Serious adverse events will be forwarded to FDA by the IND Sponsor (Safety Project Manager IND Office) according to 21 CFR 312.32.

It is the responsibility of the PI and the research team to ensure serious adverse events are reported according to the Code of Federal Regulations, Good Clinical Practices, the protocol guidelines, the sponsor's guidelines, and Institutional Review Board policy.

Investigator Communication with Supporting Companies:

Expedited reporting by investigator to BMS

Serious adverse events (SAE) are defined above. The investigator will inform BMS of any SAE within 24 hours of being aware of the event via email and/or fax.

- All SAEs should be reported via confirmed facsimile (fax) transmission, or scanned and reported via electronic mail to:

SAE Email Address: [contact]

SAE [contact]

All pregnancies will also be reported.

Reporting of adverse event information following study completion

Collection of safety information following the end of investigational product administration is important in assisting in the identification of possible delayed toxicities or withdrawal effects. All SAEs must be collected which occur within 100 days of discontinuation of dosing or completion of the patient's participation in the study if the last scheduled visit occurs at a later time.

'Expectedness': AEs can be 'Unexpected' or 'Expected' for expedited reporting purposes only. 'Expected' AEs (the ASAE) are ***bold and italicized*** in the CAEPR.

Attribution of the AE:

Definite – The AE *is clearly related* to the study treatment.

Probable – The AE *is likely related* to the study treatment.

Possible – The AE *may be related* to the study treatment.

Unlikely – The AE *is doubtfully related* to the study treatment.

Unrelated – The AE *is clearly NOT related* to the study treatment.

- Physician or designee will assign attributions.
- Adverse events will be captured in CORE.
- CTC version 4.03 will be used for this trial.
- PDMS will be used as the case report form for this study.

Pregnancy Statement

All women of childbearing potential MUST have a negative pregnancy test within 24 hours prior to receiving the investigational product. If the pregnancy test is positive, the patient must not receive investigational product and must not be enrolled in the study.

During the course of the trial, all patients of childbearing potential should be instructed to contact the treating physician immediately if they suspect they might have conceived a child. In addition, a missed or late menstrual period should be reported to the treating physician. If a female patient or the treating physician suspects that the female patient may be pregnant prior to administration of study drugs, the study drugs must be withheld until the results of a pregnancy test are available. If pregnancy is confirmed the patient must not receive study medications and must be withdrawn from the study. Throughout the entire pregnancy, additional contact should be made with the patient, and in some cases with the healthcare provider, to identify spontaneous abortions and elective terminations, as well as any medical reasons for elective termination. In addition, the study investigator should include perinatal and neonatal outcome. Infants should be followed for a minimum of 4 weeks.

If a male patient is suspected of having fathered a child while on study drugs, the pregnant female partner must be notified and counseled regarding the risk to the fetus.

In addition, the treating physician must follow the course of the pregnancy, including prenatal and neonatal outcome. Infants should be followed for a minimum of eight weeks.

Upon live-birth delivery, the minimum information that should be collected includes date of birth, length of pregnancy, sex of infant, major and minor anomalies identified at birth. Outcomes can be obtained via maternal interviews, medical record abstraction, or a combination of these methods. All serious adverse event reports relating to the pregnancy, including spontaneous abortion, elective abortion and congenital anomalies, should be forwarded to the FDA & BMS.

13.0 Informed Consent

The investigator is responsible for obtaining written, informed consent(s) from each patient interested in participating in this study prior to conducting any study-related procedures. Written informed consent should be obtained after adequate, thorough and clear explanation of the aims, methods, objectives, and potential hazards of the study as well as any use of the patient's genetic information from the study. The investigator must use the most current IRB-approved consent form for documenting written informed consent. Each informed consent will be appropriately signed and dated by the patient and the person obtaining consent. The investigational site must retain the original signed consent and provide a copy to the patient.

14.0 Correlative Studies

Correlative studies will be considered exploratory and will be performed whenever possible. Bone marrow and blood samples will only be collected on patients who consent to protocols: LAB01-473 and PA13-0291. If a patient's baseline correlative bone marrow sample is not collected for any reason, no additional correlative bone marrow or blood samples will be collected on the patient. Additionally, any samples that

are missed are not considered a protocol deviation.

Gene sequencing. Patients not consented through the Apollo program (PI [name]) will be offered consenting under protocol LAB03-473 at baseline and their genomes will be sequenced using that platform. 5 cc of blood in a green tube will be required for this analysis. If the patient participates on LAB01-473, the following samples will be collected at the specified time points:

- Bone Marrow aspirate: will be baseline, C1D28, thereafter every 3 cycles, at time of best morphological response and at progression.
- Peripheral Blood: screening, prior to each dose of study drug during the first 3 cycles, at time of best morphological response, and at progression.

Immune assessment. Tumor tissue, blood samples and bone marrow aspirate will be collected on a separate IRB approved laboratory protocol (PA13-0291) for immune monitoring as previously published,¹⁸⁻²¹ under the supervision of the Immunotherapy Platform. In tumor tissues, immunohistochemical studies will be performed to evaluate tumor and immunological cell markers such as CD4 and CD8 T cells. In peripheral blood, we will also evaluate tumor and immune cell populations including but not limited to CD4 and CD8 T cells in pre and post therapy samples.

Peripheral blood. Up to 150 mL (within 24 hours) of peripheral blood will be collected under an IRB-approved laboratory protocol (PA13-0291) for testing of biomarkers described in this clinical protocol at the following time points, if the patient agrees to participate on PA13-0291:

- At screening
- Prior to each dose of study drug during the first 3 cycles. On days when both Nivolumab and Liriumab are administered, a blood sample will only be collected prior to the Nivolumab dose.
- At time of best morphological response
- At progression

The treating physician or designee will have the option to cancel the laboratory protocol collection for patient safety without protocol deviation.

Because we will use a number of different assays, the variability of which is not necessarily established, the intention of the correlative studies is not to draw statistical conclusions in terms of the optimal biological dose of the agents studied here. Rather, they should be considered pilot studies that will help understand the in vivo mechanism of action of the agents studied, and may help in the development of future studies of this or other combinations.

